- 2) Please confirm you will secure an MTA through the appropriate office (JHTV or ORA) prior to transfer.
(See: <https://ventures.jhu.edu/technology-transfer/material-transfer-agreements/>.)
- 3) If the biospecimens you intend to transfer were obtained through clinical or research procedures at Johns Hopkins and “Other” is selected in Item 4, Section 23, please submit the following items in that Section:
 - a. A pdf version of a completed JHTV Online “Material Transfer Agreement Request Form for Outbound Material” <https://ventures.jhu.edu/technology-transfer/material-transfer-agreements/> OR a copy of the COEUS PD (Proposal Development Summary).
 - b. A completed Biospecimen Transfer Information Sheet https://www.hopkinsmedicine.org/institutional_review_board/forms/.
 - c. A signed and dated “De-identified Human Subject Certification” https://www.hopkinsmedicine.org/institutional_review_board/forms/
 - d. Approval documents from recipient site, if applicable.
 - e. Copies of the consent forms associated with the IRB protocols under which the biospecimens were collected, with language appropriate to this transfer highlighted.
 - f. The name of the specialist you are working with in ORA to complete a contract/MTA.

Please see the following website for more information about transferring human biospecimens to outside entities:
https://www.hopkinsmedicine.org/institutional_review_board/news/announcement_transfer_human_biospecimens_outside_entities.html.

REFERENCES

Date: 2/1/2023
Principal Investigator: [name]
Application Number: IRB00310939

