The primary objective of this proposal is to evaluate the feasibility and acceptability of a virtual group augmentation of standard individual well-child care. The virtual group session is designed to provide (1) an introduction to ancillary clinic and community services, and (2) Provide an opportunity for psychoeducation and discussion about psychosocial factors impacting parents of infants, including postpartum depression. The aims of the session are to (1) Increase participant knowledge about perinatal depression and the rationale for PPD screening in the general pediatric setting; (2) Decrease stigma about engaging in mental health treatment; and (3) Increase knowledge of available clinic and community resources related to addressing perinatal depression and social needs.

3. Background (briefly describe pre-clinical and clinical data, current experience with procedures, drug or device, and any other relevant information to justify the research)

This project builds upon other work that we have done with the Baltimore Latino community, and specifically with perinatal Latinas. This work includes (1) Formative research to inform a depression stigma campaign in Baltimore (IRB00211051, PI: [name]) which led to the development of a website that includes (a) accessible, Spanish-language information about depression; (b) video testimonials of community members who experienced depression (<https://www.fortalecebaltimore.org/historias>); and (c) Information about local resources. Our team also has experience successfully implementing virtual group discussions about psychosocial topics (IRB00186999, PI: [name]).

4. Study Procedures

- Study design, including the sequence and timing of study procedures (distinguish research procedures from those that are part of routine care).

Design Overview: The current study is designed as an open/single-arm pilot of the intervention (no comparison arm for this initial/preliminary study, which is also being offered as a clinic service).

Population and recruiting: There will be two categories of study participants: (1) Spanish-speaking parents of infants (<6 months) attending Johns Hopkins Bayview Medical Center's Children's Medical Practice for pediatric primary care/infants of those parents and (2) Intervention facilitators. We aim to recruit up to 60 parent participants (with 60 corresponding infant records reviewed) and up to 10 provider/stakeholder participants

Recruitment procedures:

Date: 2/1/2023

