Research staff will review electronic medical records (EMR) for children of participants from Bayview Medical Center Children's Medical Practice (CMP) to examine healthcare utilization and related health outcomes. We will look at the child's medical record at infant age 12 months.

Participant/Infant data collected using EPIC will include:

- Patient demographics (age, gender, race/ethnicity, language, insurance coverage)
- Up-to-date with age-appropriate, on-time well-child visits
- Chief complaint/reason for episodic visits
- Number of ED or urgent care visit reports in chart and reason for visits
- Visit Diagnoses and Problem List diagnoses
- Number of documented visits with the clinic family support services and primary reason for the visit
- BMI or weight-for-length percentile
- My Chart enrollment
- # of My Chart encounters documented
- Completion and results of recommended psychosocial screening (maternal depression, social needs)
- Parent participation in clinic psychosocial programming offered by the clinic (e.g. support groups, parenting and stress management interventions)

Date: 2/1/2023
Principal Investigator: [name]
Application Number: IRB00310939

b. If your study involves data/biospecimens from participants enrolled under other research studies with a written consent or under a waiver of consent, please list the IRB application numbers for those studies. Please note: Certificate of Confidentiality (CoC) protections applied to the data in source studies funded by NIH or CDC will extend to this new study if the funding was active in 2016. If this situation applies, Section 36, question 6 in the application will need to be answered “Yes” and “Hopkins Faculty” should be selected in question 7. No other documents are required. **N/A**

c. Study duration and number of study visits required of research participants.

For Parents, there will be 4 contact points with research staff over approximately 6-8 months, as detailed below

- (1) At the time of consent, complete a questionnaire prior to participation in group session this will be completed over the phone or via zoom, as we have successfully done in other studies providing intervention or preventive intervention about maternal depression (IRB00186999)
- (2) Attendance at the virtual group information session (60-75 minutes, sessions will be offered monthly at the clinic), prior to infant age 6 months

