- (3) Complete post- intervention questionnaire and interview (scheduled by phone/zoom after the session) approximately 1-2 weeks post-session
- (4) Complete brief questionnaire at 6 months post-session (scheduled by phone).

Infant medical record review will occur through the 12-month (or equivalent visit-allowing 18 months for delayed well-child visits)

For clinic staff, the study duration will be a total of up to 1.5 years. In addition to having video group sessions observed by research staff, there will be up to 4 contact points with research staff. Associated visits include:

- (1) At the time of consent, complete baseline questionnaire
- (2) Completion of feasibility and appropriateness measures after delivery of 1st, 3rd and 6th sessions.
- (3) Completion of up to 3 semi-structured interviews (after delivery of first session and up to 2 more times over a 1.5 year period). We will attempt to conduct interviews at the same time as the feasibility measures but will schedule as per the preference and availability of staff.

The content and modality of assessments are shown in Table 1 above; specific measures are attached to the IRB protocol.

d. Blinding, including justification for blinding or not blinding the trial, if applicable.

Date: 2/1/2023
Principal Investigator: [name]
Application Number: IRB00310939

N/A

- e. Justification of why participants will not receive routine care or will have current therapy stopped.
N/A, this is offered as a clinic service in addition to routine care
- f. Justification for inclusion of a placebo or non-treatment group.
N/A, being conducted as a single arm pilot
- g. Definition of treatment failure or participant removal criteria.
Participant removal criteria include: development of parent condition that would preclude participation in group discussions clinically inadvisable; or parent preference to discontinue/exit group discussion prior to its conclusion. Staff will be removed from the study if they prefer to discontinue participation or if they no longer facilitate sessions.
- h. Description of what happens to participants receiving therapy when study ends or if a participant's participation in the study ends prematurely.
As this is a single session intervention delivered as an adjunct to routine well-child care, no additional actions are taken/required to be taken
- i. If biological materials are involved, please describe all the experimental procedures and analyses in which they will be used.
N/A

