5. Inclusion/Exclusion Criteria

Parent inclusion criteria

- Parent of infant <6 months attending JHBMC CMP for pediatric primary care
- Parent Identifies Spanish as preferred healthcare language (as sessions will be offered in Spanish)
- Felt not to have a contraindication to participation (e.g., condition in the parent that would preclude the ability to reasonably participate in a virtual group session) at the initial social work assessment
- For the purposes of the study, mothers are considered the study participants and fathers are not considered study participants. However, fathers may participate in the video information sessions

Infant inclusion criteria:

infant <6 months attending JHBMC CMP for pediatric primary care

Staff Inclusion criteria

Co-facilitating or participating in delivery of virtual information session

6. Drugs/ Substances/ Devices

Date: 2/1/2023
Principal Investigator: [name]
Application Number: IRB00310939

- a. The rationale for choosing the drug and dose or for choosing the device to be used.
N/A
- b. Justification and safety information if FDA approved drugs will be administered for non-FDA approved indications or if doses or routes of administration or participant populations are changed.
N/A
- c. Justification and safety information if non-FDA approved drugs without an IND will be administered.
N/A

7. Study Statistics

- a. Primary outcome variable.

Feasibility of virtual group augmentation will be assessed by:

- Reach (number approached who attend)
- Provider/stakeholder survey (Feasibility of Intervention Measure) (7)
- Provider/Stakeholder and parent semi-structured interview

Acceptability of virtual group augmentation will be assessed by

- Acceptability of Intervention Measure (completed by parents) (7)
- Intervention Appropriateness Measure (completed by staff/stakeholders) (7)
- Satisfaction survey (See supplemental study documents)
- Semi-structured interviews with parents and providers/stakeholders (see supplemental study documents)

- b. Secondary outcome variables.

Parent-completed

- Stigma Concerns About Mental Health Care (8)
- PPD Knowledge Measure (adapted from Rapid Risk Factor Surveillance Scale) (9)
- (Adapted) Personal Stigma Scale (8)
- Intention/Willingness to seek PPD tx if needed (see supplemental study documents)
- Intention to engage in own primary care (see supplemental study documents)

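### The infant chart review collects nothing that separates a transfer of care from missed visits, and it counts service use without observation time

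*Combined protocol and SAP*

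**What the plan says.** All references are to the combined protocol and SAP.

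- **Who is reviewed.** Section 4 (population and recruiting) plans for "up to 60 parent participants (with 60 corresponding infant records reviewed").
- **Source.** Section 4a: "Research staff will review electronic medical records (EMR) for children of participants from Bayview Medical Center". No outside record source is named.
- **When.** Section 4a: "We will look at the child's medical record at infant age 12 months". Section 4c is wider: "Infant medical record review will occur through the 12-month (or equivalent visit-allowing 18 months for delayed well-child visits").
- **What is abstracted.** The section 4a list includes "Up-to-date with age-appropriate, on-time well-child visits" and "Number of ED or urgent care visit reports in chart and reason for visits", together with numbers of family-support visits and MyChart encounters. It has no field for last encounter, transfer of care or time under observation.
- **Eligibility.** Section 5 asks for an "infant <6 months attending JHBMC CMP for pediatric primary care". No condition of continued attendance follows.
- **Analysis.** Section 7c plans summary statistics and gives no denominator or missing-data rule for the chart items. Sections 7a and 7b do not list those items among the primary or secondary outcomes.

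**The concern.** An infant can enter in the first months of life, move to another practice, and still have a chart to review at 12 months. That chart would hold no later well-child visits, and neither would the chart of an infant whose family simply stopped attending. The abstracted data cannot tell the two apart. The counts have a related problem: a chart that stopped accruing at 4 months and one that ran to 12 months both yield a bare number.

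The two errors flatter and harm different items. Well-child adherence would look worse than it is, while emergency and urgent care use would look lower than it is. Section 4a gives the purpose of the review as examining healthcare utilisation and related outcomes, and section 9a names better engagement in well-child care as a possible benefit. The well-child item is the chart measure that speaks to that benefit.

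Timing also matters. Under section 8d, child identifiers are removed from the database once the chart has been reviewed. Transfer status not abstracted at the review would then be hard to recover.

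**Working it through.** The plan states no transfer rate, expected up-to-date rate or expected visit rate, so there is no figure of its own to reproduce. The arithmetic below is an illustration on stated assumptions.

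**Inputs**

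- From the documents: up to 60 infant records; review at 12 months.
- Assumed: share leaving t = 5%, 10% or 20% (3, 6 or 12 of 60); true up-to-date rate p = 80%, the same in leavers and stayers; departure at 4 months of age; constant visit rate; no outside reports reaching the chart after departure.

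**Well-child status**

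If leavers stay in the denominator and are read as not up to date, the observed rate is p × (1 − t). If they are treated as unknown, the rate lies between p × (1 − t) and p × (1 − t) + t.

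| Leaving | Observed rate | Fall from 80% | Bounds, leavers unknown |
|---|---|---|---|
| 5% (3) | 0.80 × 0.95 = 76% | 4 points | 76% to 81% |
| 10% (6) | 0.80 × 0.90 = 72% | 8 points | 72% to 82% |
| 20% (12) | 0.80 × 0.80 = 64% | 16 points | 64% to 84% |

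The fall is p × t. With p between 70% and 90% it is 3.5 to 4.5 points at 5% leaving, 7 to 9 at 10%, and 14 to 18 at 20%. Among infants still followed, the rate stays at 80% under these assumptions.

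**Counts of service use**

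A leaver contributes m of 12 months, so the understatement of the total is t × (12 − m)/12. For departure at 4 months:

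- 5%: 0.05 × 8/12 = 3.3%
- 10%: 0.10 × 8/12 = 6.7%
- 20%: 0.20 × 8/12 = 13.3%

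Check by infant-months at 10%: 54 × 12 + 6 × 4 = 672 of 720, or 93.3%. Dividing the count by 672 rather than 720 removes the shortfall.

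The result depends on when infants leave. At 10% leaving, departure at 3 months gives 0.10 × 9/12 = 7.5%, and departure at 6 months gives 0.10 × 6/12 = 5%. If use is heavier in the early months, the understatement is smaller.

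**Does the 18-month allowance resolve it?**

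It gives a late visit up to 6 more months (18 − 12) to appear. A transferred infant's visits may never appear in this chart, so late and transferred infants remain indistinguishable. It may also make observation time differ between infants who stay, which is a further reason to report counts per month.

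**The case against.** The strongest objection is that the documents give no scoring rule for infants who leave. A reader might infer that the plan scores them as non-adherent, but section 4a only lists items to abstract and section 7c promises only summaries. The misreading is therefore a risk left open by silence. This stands, and the point is conditional on summarising the listed items for all enrolled infants.

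A reader might also infer that a leaver shows no emergency or urgent care use. The documents do not support that. The item counts reports in the chart; visits before departure stay there, and outside reports may still arrive. The error is an under-count.

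The consequence is limited too. The chart items are outside sections 7a and 7b, no effect estimate or test uses them, and section 7c says the pilot is not powered for differences. It would be wrong to conclude that the feasibility or acceptability findings are compromised.

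Some instruments are not in the document. Section 4a says the 6-month questionnaire covers service utilisation, and section 4c says specific measures are attached to the IRB application. One may already ask where the infant is seen. The abstraction list may also not be exhaustive. Both points are fair, but nothing in the text shows that transfer is captured.

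Finally, an ill-chosen remedy could add bias. Restricting the denominator to active patients, judged by recent encounters, would drop true non-attenders and inflate adherence. This stands and shapes the fix. Section 4g is not evidence either way: its parent removal criteria concern the group discussion and do not govern the chart analysis.

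**Conclusion.** The gap is real and modest. As written, the chart review cannot distinguish transfer from missed visits, and its counts lack observation time. If all enrolled infants are summarised from the practice's chart, well-child adherence may be understated by 4, 8 or 16 points at 5%, 10% or 20% leaving, and counts by about 3%, 7% or 13%. These sizes rest entirely on the assumed transfer rates, 80% truly up to date, departure at 4 months and a constant visit rate; the documents supply none of them. With one arm, no comparison group would show how much of a low well-child figure is due to transfer. The primary conclusions are unaffected. The change is still worth making before abstraction, because it is cheap and the missing information could not readily be rebuilt afterwards.

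**What to change.** **Collect**

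- Two abstraction fields: date of last encounter at the practice, and documented transfer of care with its date.
- One item on the existing 6-month call: does the infant still attend the practice?

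**Report**

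- The number of infants with confirmed transfer.
- Well-child status for all infants, with confirmed transfers shown as unknown (lower and upper bounds).
- As a second presentation, well-child status excluding only confirmed transfers. Infants who merely stopped attending stay in the denominator.
- Emergency or urgent care, family-support and MyChart counts per month observed, ending observation at confirmed transfer and otherwise at the review age.

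**Cost and limits**

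The cost is slightly more abstraction, one extra question, and a smaller denominator in the second presentation. No new contact is needed. Some transfers will still be missed. For example, an infant whose parent attends a session at infant age 1 month is called at 7 months, leaving 5 months to the 12-month review in which an undocumented transfer would go unseen. The report should say so.

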- *Introduction and discussion of purpose of the session (5 minutes)*
- *Overview of services available at the clinic & procedures, reminder of MyChart (5 minutes total)*
- *Insurance, entitlement programs – (10-15 minutes total)*
- *Postpartum depression information, discussion of screening (30-40 minutes)*
 - o *PPD information: show video and discussion afterwards*
 - *Video : (5 minutes)*
 - *Reflection/discussion about video 10 minutes*
 - *Additional core messages: 10 minutes*
 - *Prevalence and signs of PPD*
 - *Discussion of PPD Screening procedures, rationale for screening at pediatric office*

Date: 2/1/2023
Principal Investigator: [name]
Application Number: IRB00310939

- *Discussion of self care & social support*
- *Community resources (5 minutes, link to clinic website also sent by text)*
 - *Medical Care*
 - *Mental Health*
 - *Sources of information (clinic website)*

The video shown will be a testimonial developed by JHBMC's Centro Sol for a local mental health stigma campaign (Formative research for the campaign conducted as part of IRB00211051), video to be shown is available at <https://www.fortalecebaltimore.org/historias>

After the session, ideally within 2 weeks post-session, the research team will collect post-session measures and semi-structured with parent participants and conduct post-intervention interviews with participants. The post session interviews may be conducted at the same time as the surveys, or at a separate time, depending on the preference of the participant.

6 months after the session, the research team will administer questionnaires over the phone assessing feedback about the intervention, physical and mental health services utilization, and re-administering measures of stigma, depression knowledge, intention to seek PPD treatment if needed, intention to seek primary health care, and self-efficacy to manage negative emotions. A summary of measures used and timing is included in **Table 1** below.

For clinic staff/stakeholder participants:

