- Mental health and primary care services utilization (from National Latino and Asian American Study) (10)
- Self-reported use of clinic website and/or services
- Self-reported mental health and primary care service utilization

- c. Statistical plan including sample size justification and interim data analysis.
Summary statistics will be used to describe participant characteristics, intervention implementation metrics, and outcome measures. We will assess mean changes in selected parent measures (Stigma Concerns about Mental Health Care, Depression Knowledge, Intention/willingness to seek PPD treatment if needed). This is a pilot study designed to assess feasibility and acceptability of the intervention and is not powered to detect differences in outcome measures.

Date: 2/1/2023
Principal Investigator: [name]
Application Number: IRB00310939

For qualitative data, the interviews will be digitally-recorded and then transcribed and translated (if applicable). Prior to analysis names and other identifying factors in the interview will be removed or assigned a pseudonym. We will explicitly ask for permission to record interviews, and will not audio record interviews if any participant does not feel comfortable with doing so. After completing an interview or visit, the digital file will be downloaded to a Safe Desktop site. Files will not contain identifying information but will be labelled with the participant unique identifying code. Audio recordings will be deleted from digital recorders as soon as successful downloading of the file has been confirmed. Fidelity checklists and observation notes will also be included in the qualitative data collection and analysis.

During analysis of qualitative study data, the study team will develop preliminary themes iteratively and through consensus. At least two investigators will independently code each text segment and then generate analytic conclusions with other study team members.

d. Early stopping rules.

As we are not using any drugs or medical devices we do not anticipate the need for early stopping except when desired by the participant.

8. Risks

a. Medical risks, listing all procedures, their major and minor risks and expected frequency.

i. Risks associated with completing measures and interviews: Completing measures about sensitive topics (eg depression), or participating in interviews may be stressful for the participants.

ii. Risks associated with participation in group discussions

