-Symptom/situation disclosure: it is possible that parent participants will disclose psychosocial circumstances warranting concern and evaluation and that the provider may have difficulty managing multiple disclosures.

-Group dynamics: it is possible that parents will feel uncomfortable participating in group discussions

-There are risks that other group members may discuss what happened in the group outside of that setting

iii. Risks associated with Observation process

Reactivity and Observer Bias – We are mindful of the reactivity effect (i.e. study participants' behavior being influenced by the presence of observers). We note that several staff typically are present in other group interventions in the clinic as well as in the obstetric clinic (facilitator, co-facilitator, MA/Nursing staff), which we believe may “normalize” the presence of additional staff to

Date: 2/1/2023
Principal Investigator: [name]
Application Number: IRB00310939

some degree. We will utilize unobtrusive observation and note-taking techniques to minimize this effect. Finally, we will regularly reinforce with group facilitators that the observation process will not affect job performance/evaluation.

iv. Risks to confidentiality- Virtual discussion Risks associated with virtual group discussion, there is risk that discussion via Zoom groups may be “hacked”- this risk will be minimize by use of JHU professional accounts with password protection (a separate password for each group discussion). Virtual groups are conducted as part of routine clinical care at CMP (e.g. parent support groups) and research studies (, thus we do not anticipate additional risk related to research.

b. Steps taken to minimize the risks.

Completing research measures or interviews: The PI or the trained research assistant will be available at all times while the participant is filling out questionnaires or participating in interviews. Participants will be reminded that they do not have to answer any questions with which they feel uncomfortable. Should a participant become distressed, the study staff member can provide reassurance, evaluate his/her concerns, and remind participant that he/she may stop at any time. The participant will also be asked if he/she would like to discuss concerns with on-site clinic social work or mental health staff or with the Principal Investigator, [name], a bilingual psychiatrist.

Risks associated with participation in group discussions

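### Section 4.g lists leaving the group session early as a removal criterion; read literally, mothers who walk out are never asked how acceptable they found it.

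*Combined protocol and SAP*

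**What the plan says.** Section 4.g gives two removal criteria for parents: a condition in the parent that rules out taking part in the group, and "parent preference to discontinue/exit group discussion prior to its conclusion". The sentence does not state what the mother is removed from. The next sentence, on staff, does: "Staff will be removed from the study if they prefer to discontinue participation or if they no longer facilitate sessions".

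On timing, the study design part of section 4 says: "After the session, ideally within 2 weeks post-session, the research team will collect post-session measures". Table 1 places the parents' acceptability measure, satisfaction questionnaire and qualitative interview in the post-session column only, and section 4.c puts that contact at about 1-2 weeks. A 6-month phone survey also asks for feedback on the session.

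Section 7.a makes the parent-completed acceptability measure, the satisfaction survey and the parent interview primary outcomes for acceptability. The parent interview also counts towards feasibility. Reach, another primary outcome, is the number approached who attend; partial attendance is not defined.

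For analysis, section 7.c says: "Summary statistics will be used to describe participant characteristics, intervention implementation metrics, and outcome measures". It defines no analysis set, no denominator for acceptability and no handling of early exits. Section 8.a.ii lists as a risk that "it is possible that parents will feel uncomfortable participating in group discussions".

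**The concern.** For an acceptability outcome, walking out may be the clearest negative response a participant can give. If walking out also ends her participation, the outcome is measured only in mothers partly selected on that same outcome, and the result would probably be too favourable. The protocol itself foresees discomfort in the group, so a link between exit and acceptability is plausible. Some mothers will leave for unrelated reasons, such as the infant needing care, and then little bias follows. Without asking leavers, the team cannot tell which case applies.

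The time of exit matters too. By the session outline, 20-25 minutes of other content precede the postpartum depression block. A mother who leaves in that time could count as attending in reach, would have received none of the depression content, and would be missing from the acceptability results.

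The matter is limited to what mothers report themselves. Reach and the staff ratings after a first session do not depend on mothers staying to the end.

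**Working it through.** **No figure in the plan to reproduce.** The documents give no exit rate, no satisfaction rate and no endpoint defined as a percentage satisfied. The ceiling of 60 parents has no calculation behind it. The check is therefore a reading of the text plus an illustration of size.

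**Reading the text.**
1. Section 4.g: exiting the discussion early is a removal criterion.
2. Same paragraph: for staff, removal is from the study. For parents the object is left out.
3. Table 1 and section 4.c: no parent-reported acceptability is collected before or during the session.
4. From 1 to 3, on the study-level reading, an early leaver gives no acceptability measure, satisfaction survey or interview, and no 6-month feedback.
5. Nothing in the protocol text says that early leavers stay in follow-up.

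**Time before the depression block** (session outline, section 4): introduction 5 + clinic services 5 + insurance 10 to 15 = 20 to 25 minutes.

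**Size.** Let p be the share of joiners who exit, r the result in stayers and s the result in leavers. The result for all who joined is (1 − p)r + ps, so

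overstatement = r − [(1 − p)r + ps] = p(r − s).

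Assume r = 90%, all 60 join, and p = 5%, 10% or 20%. The sampling half-width is 1.96 × √(0.9 × 0.1 / n), with n the number of stayers. Entries are percentage points.

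| Exit share | Leavers / stayers | s = 0% | s = 45% | s = 90% | 95% half-width |
|---|---|---|---|---|---|
| 5% | 3 / 57 | 4.5 | 2.25 | 0 | 7.8 |
| 10% | 6 / 54 | 9.0 | 4.5 | 0 | 8.0 |
| 20% | 12 / 48 | 18.0 | 9.0 | 0 | 8.5 |

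With s = 0 the all-joiner results would be 85.5%, 81.0% and 72.0%, against 90% reported from stayers.

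**Check in whole mothers.** Stayers only, against all 60 with leavers counted as all negative or all positive:
- 3 leave: 51/57 = 89.5%, against 51/60 = 85.0% to 54/60 = 90.0%
- 6 leave: 49/54 = 90.7%, against 49/60 = 81.7% to 55/60 = 91.7%
- 12 leave: 43/48 = 89.6%, against 43/60 = 71.7% to 55/60 = 91.7%

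The worst-case gaps are 4.5, 9.1 and 17.9 points, which agree with the formula apart from rounding to whole mothers.

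**When the bias exceeds sampling error.**
- At 5% exit, never: at most 4.5, against 7.8.
- At 10%: 0.10 × (0.90 − s) > 0.080 requires s below about 10%.
- At 20%: 0.20 × (0.90 − s) > 0.085 requires s below about 48%.

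**The case against.** The clause may be about the session only. It speaks of leaving the discussion, and it omits the reference to the study that the staff sentence contains. Section 4 plans the post-session measures for parent participants without limiting them to mothers who completed the session. No sentence says that a mother who leaves will not be contacted. Section 4.h, on premature end of participation, seems to concern care rather than data collection and settles nothing. The consent script and supplemental documents to which the protocol refers were not available for this review, and they might draw the distinction.

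Other sources could also record a walk-out. Section 7.c brings observation notes and fidelity checklists into the qualitative analysis, and section 8.b has providers complete the checklist if observation is declined. Staff ratings and interviews are acceptability outcomes as well.

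Finally, the size is wholly assumed. The 18-point end needs one mother in five to leave a single 60-75 minute session with none of them satisfied, and the plan states no acceptability threshold that these points would move.

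Much of this stands as a limit: the loss may not be intended, it touches parent self-report only, and it may be small. It does not remove the concern. The clause sits under participant removal, the adjoining sentence uses removal to mean leaving the study, and a removed mother may no longer be treated as a participant for the follow-up contact. Staff could apply the text either way. Notes on an exit do not give the mother's own rating or, necessarily, her reason. The absence of a threshold does not make a descriptive estimate of a primary outcome less exposed to selection.

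**Conclusion.** The concern holds and should be fixed. On the literal reading, section 4.g removes from a primary outcome the mothers most likely to have found the session unacceptable, and neither 4.g nor 7.c rules that reading out. Confidence is medium, because a session-only meaning is possible and the documents available do not decide it.

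The illustrative overstatement is 0 to 18 percentage points. This assumes 60 joiners, 90% satisfaction among stayers, 5-20% exit and leavers no more satisfied than stayers. It is zero if nobody leaves or if leavers rate the session as stayers do, and it exceeds sampling error only with about 10% or more leaving and much lower ratings among them. The removal of staff who stop facilitating, with no assessment planned afterwards, is a lesser point of the same kind.

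**What to change.** In section 4.g, separate leaving the session from withdrawing from the research. State that a mother who exits early:
- stays in the study unless she withdraws consent;
- counts in reach as a partial attendee, with the time of exit recorded and whether it came before the depression block;
- is still offered the post-session measures, the interview and the 6-month survey.

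In section 7.c, report acceptability for all mothers who joined a session, together with the number of early exits, the reasons given and the response rate among leavers.

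Optionally, offer staff who stop facilitating the same short feasibility and appropriateness survey once, at exit.

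The cost is one or two sentences in 4.g and 7.c, with no new instrument or visit. Under the payments already planned in section 10, each early leaver who completes everything receives $20 + $40 + $20 = $80; a staff exit survey would add $5. Some leavers will not respond, so the change reduces and describes the bias but does not remove it.
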